***Medtronic Business Restricted***

## 9. Statistical Design and Methods

### 9.1. General Aspects of Analysis

The study analysis will occur after all patients complete the 30-day follow-up and data entry error or non-reasonable values are cleaned. Data analysis will be performed by Medtronic or its designee using SAS for Windows (version 9.4 or higher, SAS Institute Inc. Cary, NC) or other widely accepted statistical or graphical software.

Statistical tests will be conducted at a two-sided alpha level of 0.05. Confidence intervals will be presented as 95% confidence intervals.

The following populations will be considered for the analysis of data for this study:

- Full Analysis Set (FAS): The full analysis set is defined as all enrolled subjects in whom the Hugo™ RAS procedure is begun (defined as the first skin incision). In the event that a subject is consented but the first incision does not occur (e.g., if the subject becomes ineligible during the timeframe between consent and the procedure day), that subject will be excluded. Also, a subject who inevitably converted (to open or conventional laparoscopic surgery) not due to the Hugo™ RAS system will be included in the safety and other descriptive analyses but excluded from the primary endpoint analysis (since the subject is not evaluable).
- Per Protocol Set (PPS): The per protocol set is a subset of the FAS including only those without any major protocol deviations. Following subjects from the FAS will be excluded from the PPS:
  - Subject who inevitably converted (to open or conventional laparoscopic surgery) not due to the Hugo™ RAS system
  - Subject did not meet Inclusion/exclusion criteria
  - Subject chooses to withdraw
  - Failure to collect required study data up to 30-day post-surgery

The FAS will be the primary analysis set for the evaluation of the primary and secondary endpoints. Statistical analysis will be performed for each analysis set. However, if all subjects complete the study per the CIP, the results can be presented regardless of the analysis set.

Subject disposition will be illustrated in a CONSORT diagram. All enrolled subjects will be included in a subject disposition table indicating reasons for exclusion from the FAS and PPS analysis sets.

Descriptive statistics will be used to present the data and to summarize the results. Continuous variables will be summarized with number of subjects (n), mean, standard deviation, median, and ranges. Categorical variables will be summarized by frequencies and percentages. The 95% confidence intervals for means and/or percentages will be also presented.

*Medtronic Business Restricted*

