### 4.2.1. Primary Objective

The primary objective is to confirm that the Medtronic Hugo™ RAS System performs as intended when used for prostatectomy or cholecystectomy. Primary endpoint is below:

- Completion rate: A proportion of subjects who completed the surgery without conversion (to open or conventional laparoscopic surgery) due to system serious malfunction, and without any major complications within 24-hour post-surgery
  - \* Major complication is defined as Clavien-Dindo grade  $\geq 3$

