### 4.2.2. Secondary Objective

The secondary objective is to assess the short-term safety outcome of the Medtronic Hugo™ RAS System when used for prostatectomy or cholecystectomy. Secondary endpoints are below:

- Overall complication rate through 30-day post-surgery: A proportion of subjects with any post-operative complication within 30-days post-surgery using the investigational device
- Major complication rate through 30-day post-surgery: A proportion of subjects with any post-operative complication classified  $\geq 3$  by the Clavien-Dindo system within 30-days post-surgery using the investigational device

*Medtronic Business Restricted*

- Readmission rate through 30-day post-surgery: A proportion of subjects hospitalized within 30 days post-surgery
- Reoperation rate through 30-day post-surgery: A proportion of subjects go through reoperation for the same indication within 30 days post-surgery
- Device deficiency rate: A proportion of subjects with any device deficiency (DD) during robotic assisted surgery using the investigational device

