**Medtronic Business Restricted**

## 5.6.2. Preparing for Surgery

- Confirming components from the system tower: Check the OR team interactive display and confirm that the arms and surgeon console needed for the surgical procedure are connected.
- Arm setup: Calibrate arms on the OR team interactive display then complete arm setup according to the Arm Setup Guide. The following steps appear in the Arm Setup Guide: Draping arm cart, attaching instrument interface, placing port in patient (refer to 5.6.3 port placement for detail), positioning arm cart at bedside, docking arm to port, and checking arm positioning.
- Endoscope setup: Place the endoscope in the endoscope adapter
- Performing minimally invasive surgery prior to RAS (as needed): Perform any non-robotic surgical procedures as needed prior to performing robotic-assisted surgery.
- Setting up the surgeon console and initial arm assignments: Complete ergonomic setup

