The detailed procedural steps are described below. The steps can vary based on surgeon's technique, preference, and patient's condition.

---

 Setup time is defined as sum of following durations: Time from the first robot arm plugged in to all arms fully calibrated, time spent to drape all robotic arms, and time from the movement of the first arm to the patient to all arms docked to ports.

 See Hugo Set-up Guide and Hugo User Guide for detailed information

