## 8.8. Subject Exit, Withdrawal or Discontinuation

Subjects have the right to refuse to participate the study as well as voluntarily withdraw from the study at any time. In case of study exit, the reason and date for study exit of all enrolled subjects will be documented on the applicable page of case report form (CRF). Subjects may be exited from the study for any of the following situations:

- Study completed (i.e., completed 30-day post-operative visit)
- Subject did not provide consent
- Subject chooses to withdraw
- Subject did not meet inclusion/exclusion criteria
- Subject did not receive surgery using the investigational device
- Subject death
- Subject lost to follow-up (i.e., up to 30-day post-operative visit)
- Unacceptable AEs
- Investigator deems withdrawal necessary (e.g., medically justified, failure of subject to maintain adequate study compliance)

All AEs must be followed until the AE has been resolved, is unresolved with no further actions planned, the subject dies or exits the study, whichever occurs first. In cases of early study exits, all data collected from the time of consent to the time of exit may be used. For subjects who complete the 30-day follow-up visit, the 30-day follow-up visit and exit visit should be combined, and CRF for both need to be completed.

*Medtronic Business Restricted*

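### A system failure that stops the Hugo procedure before first incision would be recorded but would enter no endpoint rate

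*Protocol*

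**What the plan says.** Protocol 9.1 defines the FAS as "all enrolled subjects in whom the Hugo™ RAS procedure is begun (defined as the first skin incision"). The next sentence excludes the subject "In the event that a subject is consented but the first incision does not occur", with loss of eligibility between consent and surgery as its example. SAP 7.1.3 repeats the rule. The FAS is the primary set for the primary and secondary endpoints, the per protocol set is a subset of it, and Protocol 9.1 judges success in it. SAP 7.10 bases adverse event proportions on it as well. The synopsis describes the same set more loosely, as the subjects treated with the device.

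The primary endpoint is "A proportion of subjects who completed the surgery without conversion (to open or conventional laparoscopic surgery) due to system serious malfunction" and without a major complication within 24 hours. The DD rate is "A proportion of subjects with any device deficiency (DD) during robotic assisted surgery using the investigational device".

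Protocol 5.6.2 gives the order of preparation: "Calibrate arms on the OR team interactive display then complete arm setup according to the Arm Setup Guide". The guide's steps then begin "Draping arm cart, attaching instrument interface, placing port in patient", with docking afterwards. Protocol 8.8 lists "Subject did not receive surgery using the investigational device" among the reasons for study exit.

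**The concern.** The primary objective is to confirm that the system does what it is meant to do in these two operations. A system that cannot be brought to the point of incision has not done so. Yet the FAS rule removes that subject for the same formal reason as a patient who became ineligible. A slow set-up is recorded with its reason (Protocol 8.5) and summarised (Protocol 9.3), whereas a set-up that fails outright leaves the analysis. The denominator is thus selected on the device having worked up to incision, and any bias from this favours the device.

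The margin is thin. Protocol 6.5 allows at most two non-completions among 40, so a single unclassified case could matter. The trial is single-arm and unblinded, the sponsor or its designee does the analysis, and there is no data review committee. The classification is better fixed before any such case arises.

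**Working it through.** **Inputs.** Success if the point estimate is at least 0.95 in the FAS (Protocol 9.1); 40 subjects with at most 2 non-completions (Protocol 6.5); order of preparation (Protocol 5.6.1, 5.6.2, 8.5.1, 8.5.2). The documents give no rate of device-caused non-starts; call it q per case.

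**1. The plan's own figure.** 38/40 = 0.950 meets the rule and 37/40 = 0.925 does not. The stated limit of two failures reproduces.

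**2. Which failures fall before the incision.** Power-up (5.6.1), calibration, draping and interface attachment (5.6.2) precede port placement. Docking follows it. The set-up time footnote in 8.5 includes "time from the movement of the first arm to the patient to all arms docked to ports", so part of set-up comes after incision. A docking failure leaves the subject in the FAS, and conversion because of a serious malfunction counts as non-completion.

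**3. Where a pre-incision failure would appear.**
- Disposition table and CONSORT diagram, with the reason for exclusion (9.1): yes.
- Exit reason (8.8) and DD form (10.1): yes.
- Completion rate, DD rate, other secondary rates, adverse event proportions: no, because all use the FAS or a subset of it.

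**4. Effect of counting non-starts, with 40 incised subjects.** For f failures after incision and k non-starts, the rate becomes (40 − f)/(40 + k).

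| f | Current rule | Most non-starts that still pass | First result that fails |
|---|---|---|---|
| 2 | 38/40 = 95.0% | none | 38/41 = 92.7% |
| 1 | 39/40 = 97.5% | 1: 39/41 = 95.1% | 39/42 = 92.9% |
| 0 | 40/40 = 100% | 2: 40/42 = 95.2% | 40/43 = 93.0% |

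Under the current rule every row passes, whatever k is.

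**5. If non-starts are not replaced.** Protocol 6.1 sets 40 as a minimum enrolment, and enrolment is at consent. Protocol 6.5 allows new enrolment explicitly only for conversions not due to the system. With 40 brought to surgery, one non-start cannot reverse the result: with two failures 37/39 = 94.9% fails already, and with one failure 38/39 = 97.4% and 38/40 = 95.0% both pass. Two non-starts and one failure do reverse it: 37/38 = 97.4% against 37/40 = 92.5%.

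**6. Illustration under assumed rates.** Take q from 0.4% to 3%. These are the low end and the average of the all-malfunction rates cited in 6.5, borrowed only as a range. The chance of at least one non-start before 40 incisions is 1 − (1 − q)^40: 14.8% at 0.4%, 33.1% at 1% and 70.4% at 3%.

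The chance of a changed conclusion is smaller. Assume 97% completion after incision, so that f = 0, 1, 2 have binomial probabilities 0.296, 0.366 and 0.221 (sum 0.882, the pass probability now). Then

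P(reversal) = 0.221·P(k ≥ 1) + 0.366·P(k ≥ 2) + 0.296·P(k ≥ 3),

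where P(k ≥ 2) = 1 − (1 − q)^40·(1 + 40q) and P(k ≥ 3) = 1 − (1 − q)^40·(1 + 40q + 820q²).

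- q = 0.4%: 0.221 × 0.148 + 0.366 × 0.012 + 0.296 × 0.001 ≈ 4%
- q = 1%: 0.221 × 0.331 + 0.366 × 0.063 + 0.296 × 0.009 ≈ 10%
- q = 3%: 0.221 × 0.704 + 0.366 × 0.349 + 0.296 × 0.131 ≈ 32%

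**The case against.** The strongest reply is that the case is rare, would be visible, and lies outside what the primary endpoint measures. A procedure that has not begun cannot be converted, and an incision-based set is a reasonable base for complications. A fault that is fixed, or a case that starts late, stays in the FAS and shows as a set-up delay. The 3% in Protocol 6.5 covers all malfunctions. The same section puts failure-related conversions at 0.9% on average (0.1% to 2.7%) and reports none in the Korean series. At q = 0.1% the chance of any non-start in 40 is about 4%. All of this stands, and it limits the size of the point.

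It can also be said that the exclusion sentence does not clearly reach a patient who goes on to conventional surgery, since a skin incision then does occur. That is right. The text does not say whether that incision begins the Hugo procedure. The synopsis wording points to exclusion but does not settle it, and that gap is itself part of the point.

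A reader might infer that any set-up failure escapes, or that the device's inability to start is hidden altogether. The documents support neither reading. Docking failures come after incision and count if they lead to conversion. Pre-incision failures would appear in the disposition table, the exit reason and the DD form. Nor does the wording of the DD rate by itself rule such a case out: Protocol 8.1 places set-up, take-down and DD collection in the same surgical visit. What keeps the case out is the FAS.

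What survives is that a line in a disposition table is not a count in a rate.

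**Conclusion.** The point holds for unrecoverable system failures before the first incision. They enter no planned endpoint rate, so the completion and DD rates are conditional on the system having worked up to incision. For a subject who then has conventional surgery, the classification is open and should be settled in advance.

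The size cannot be fixed from the documents, because they give no non-start frequency. One case reverses the conclusion only if 40 subjects are incised and two of them have already failed. With one failure or none, a single non-start still passes. With 97% completion after incision and non-starts replaced, the chance of a changed conclusion is about 4% to 32% for q between 0.4% and 3%. That range rests on a borrowed rate for a broader event and should be read as illustration. A reader might take the 33% to 70% chance of at least one non-start (q = 1% to 3%) as the chance of a wrong conclusion, but it is not. This is a minor, inexpensive improvement and does not by itself undermine the primary analysis.

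**What to change.** Keep the incision-based FAS and the primary success rule. In the SAP:

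1. State that a subject brought to the operating room in whom a system problem prevents the Hugo procedure from starting is classified as a device-caused non-start, even if conventional surgery follows. Show this as its own reason in the disposition table.
2. Pre-specify a sensitivity analysis of completion that adds these subjects to the denominator and scores them as not completed.
3. Pre-specify a supplementary DD rate that includes them in numerator and denominator.

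The cost is a SAP revision. DD forms, exit reasons and set-up delays are already collected, so no new visit, subject or data item is needed. The downside is a possibly less favourable supporting figure. Rewriting the protocol's own DD-rate definition would need a protocol amendment; unless that is classed as minor, Protocol 12.2 requires approval first and stops enrolment until it is given. The supplementary analysis in the SAP is the cheaper route.

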## 6.5. Sample Size Determination

To estimate the number of sample size, two things are taken into account: The number of subjects from previous studies, and the minimum number [8] to show whether the primary objective is met. We plan to include 40 patients for the study.

- Research hypotheses: The completion rate is greater than or equal to 95% (point estimate).

The completion is defined that surgery completion without conversion (to laparoscopic or open surgery) due to system serious malfunction, and without any major complications within 24-hour post-surgery. Therefore, when a subject who inevitably converted not due to the Hugo™ RAS system, it is not considered as a surgery failure as per the definition and the subject will be excluded from the primary endpoint analysis. Also, a complication within 24-hour post-surgery will not be considered as a surgery failure unless it falls under the definition of major complication.

According to previous literature on adverse events in robotic surgeries over 14 years using da Vinci, the average rates of device malfunctions and failure-related conversions was 3% (varied between 0.4% and 8.0%) and 0.9% (varied between 0.1% and 2.7%), respectively [9]. In Korea, the reported rate of system malfunctions and failures was less than 2% among over 10,000 da Vinci robotic procedure cases between 2005 to 2013. However, no cases of malfunction led to conversion to open or laparoscopic surgery [10].

---

 According to the Korean Clinical Practice Guideline for the Treatment of Prostate Cancer (The Korean Urological Oncology Society, 2020)[7], radical prostatectomy is an appropriate therapy for any patient with clinically localized prostate cancer that can be completely excised surgically, who has a life expectancy of  $\geq 10$  years, and who has no serious comorbid conditions that would contraindicate an elective operation.

 Relative contraindications for laparoscopic cholecystectomy include followings: Inability to tolerate general anesthesia due to cardiopulmonary diseases, hemodynamic instability, pregnancy (3rd trimester), malignant tumors, liver cirrhosis and portal hypertension, and intestinal adhesions (Kim & Seo. Hepato-Biliary-Pancreatic Surgery (4th ed.). 2019)

  $N \geq 30$  according to the central limit theorems

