With regards to the previous studies, the completion rate of surgery—the primary endpoint of this study—is expected to be over 90%. The study will be considered successful when the point estimate of the completion rate is greater than or equal to 95%, which is when  $\leq 2$  patients (among 40) does not reach the surgery completion. The primary endpoint is evaluated within short period (i.e., 24-hour post surgery) period so the dropout rate is not considered. Note that it is not possible to assess the surgery completion per the study definition when a subject who inevitably converted not due to the Hugo™ RAS system. In such cases, new enrollment is allowed until the minimum sample size (i.e., 40) is reached.

In summary, the estimated sample size is adequate to demonstrate the safety and performance of the investigational device regarding following reasons: (1) the estimated sample size is higher than the number of patients from recent pivotal trial (which used the same primary endpoint) of the locally commercialized product (i.e., 32; 17 prostatectomy cases and 15 cholecystectomy cases) [11, 12], and (2) the investigational device is intended to be used for the same patient population of the commercialized product.

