### 8.10. Assessment of Effectiveness

Effectiveness of the Hugo™ RAS System will be evaluated through the study primary endpoint (completion rate). Effectiveness assessment will be done on the day of surgery as below.

*Medtronic Business Restricted*

- Completion rate: A proportion of subjects who completed the surgery without conversion due to system serious malfunction, and without any major complications within 24-hour post-surgery

Surgery completion is defined if procedure is completed without conversion to open or laparoscopic surgery due to system serious malfunction per surgery record, and no major complication reported within 24-hour post-surgery period. Note that unavoidable Aes are inherent to the procedure (see Section 10.2 for details) are not included in this definition of major complication within 24-hour post-surgery.

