**Medtronic Business Restricted**

What is classified?	Who classifies?	Classification parameters
		
 
▪ the event follows a known response pattern to the medical device (if the response pattern is previously known)
 
▪ the discontinuation of medical device application (or reduction of the level of activation/exposure) and reintroduction of its use (or increase of the level of activation/exposure), impact on the event (when clinically feasible)
 
▪ other possible causes (e.g., an underlying or concurrent illness/clinical condition or/and an effect of another device, drug or treatment) have been adequately ruled out
 
▪ harm to the subject is due to error in use
 
▪ the event depends on a false result given by the investigational device used for diagnosis, when applicable
 

Severity	Investigator	
Severity will be assessed and categorized as "Negligible", "Minor", "Moderate", "Major", or "Critical".
 
 
- Negligible: No/minimal impact on the patient's health condition
 
- Minor: Presence or risk of temporary problem on the patient's health condition, regardless of underlying diseases of the patient
 
- Moderate: Presence or risk of reversible reduction in function (sensory, motor, physiological, or cognitive) on the patient's health condition, regardless of underlying diseases of the patient
 
- Major: Presence or risk of permanent reduction in function (sensory, motor, physiological, or cognitive) on the patient's health condition, regardless of underlying diseases of the patient
 
- Critical: Presence or risk of death or serious irreversible impairment in function (sensory, motor, physiological, or cognitive) on the patient's health condition, regardless of underlying diseases of the patient
 

Seriousness	Investigator, Sponsor	SAE, SADE, DD with SADE potential
Expectedness	Sponsor	UADE, USADE
Diagnosis	Investigator	Based on presenting signs and symptoms and other supporting data
	Sponsor	MedDRA term (System Organ Class and Preferred Term) assigned based on the data provided by the investigator

In addition, all post-operative AEs will be classified by the investigator according to the Clavien-Dindo classification system below in Table 10.

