**Medtronic Business Restricted**

**CONFIDENTIAL**

056-F275 Rev E Clinical Investigation Plan Template

	
 
- Investigational device: Added images of surgeon console, arm carts, and system tower, removed description on the comparison between the investigational device and locally commercialized devices, added a summary of the instructions for use
 
- Inclusion criteria: Added detailed description for gallbladder polyps
 
- Exclusion criteria: Removed BMI <math>\geq</math> 35, ECOG Performance Status <math>\geq</math> 2
 
- Sample size: Revised according to previous research results and updated the target performance
 
- Study measurements: Changed port placement and arm positioning figures for cholecystectomy
 
- Study endpoints: Updated wording of primary endpoint definition (i.e., “any system-related major complication” to “any major complication”)
 
- Statistical methods: Added details in the definition of full analysis set
 
	
5.0	
Minor changes are made upon MFDS amendment request on version 4.0:
 
 
- Investigational device: Inserted a paragraph that the system does not support hospital network or other Ethernet connectivity
 
- Statistical methods: Added details in the analysis set definition
 
	[name], Senior Clinical Research Specialist

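### A patient converted for a non-Hugo reason who has a major complication within 24 hours has already failed the primary endpoint, yet the plan excludes and may replace that patient

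*Protocol*

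**What the plan says.** Protocol 4.2.1 and SAP 7.9 define completion as surgery finished without conversion due to serious system malfunction and "without any major complications within 24-hour post-surgery", where major means Clavien-Dindo grade 3 or higher. Protocol 8.10 restates both conditions, including "no major complication reported within 24-hour post-surgery period", and leaves out only adverse events regarded as unavoidable. The complication condition does not depend on cause. The version history (protocol 15, version 4.0) agrees: "Updated wording of primary endpoint definition (i.e., “any system-related major complication” to “any major complication".

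Conversions not due to the Hugo system are handled separately. Protocol 6.5 and SAP 6 say of such a subject that "it is not considered as a surgery failure as per the definition and the subject will be excluded from the primary endpoint analysis". Protocol 9.1 and SAP 7.1.3 repeat that such a subject is "excluded from the primary endpoint analysis (since the subject is not evaluable", and remove the same subjects from the PPS. Protocol 6.5 adds that "it is not possible to assess the surgery completion per the study definition" and then: "In such cases, new enrollment is allowed until the minimum sample size (i.e., 40) is reached".

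Protocol 9.1 decides success by the FAS point estimate alone, at 0.95 or more. Protocol 6.5 translates this into at most 2 non-completers among 40.

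**The concern.** The exclusion rests on the outcome being unknown. That is reasonable for a non-Hugo conversion with an uneventful first day. It is not true if the same patient has a grade 3 or higher complication within 24 hours, because breaching one of two required conditions settles the endpoint.

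Followed exactly, the plan removes a known failure from numerator and denominator and allows another patient in its place. With a margin of only two failures, one patient can decide the result of a pivotal trial, and that patient is one with a serious early complication. No planned analysis of the primary endpoint would contain the patient, since the PPS drops the same subjects. The only sensitivity analysis mentioned is optional and has imputation of missing data as its example.

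**Working it through.** **Inputs.** N = 40, success at a point estimate of 0.95 or more, at most 2 failures (protocol 6.5 and 9.1). Exclusion and replacement as described above.

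**The plan's own figure.** The largest f with (40 − f)/40 ≥ 0.95 is f = 2: 38/40 = 95.0% passes and 37/40 = 92.5% fails. The stated limit is reproduced.

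**Who is affected.** The subject needs an unavoidable non-Hugo conversion and also a post-operative grade 3 or higher event within 24 hours. Protocol 10.2 says "all post-operative AEs will be classified by the investigator according to the Clavien-Dindo classification system", so an intraoperative event that forces the conversion does not by itself qualify.

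**One such subject, by number of other failures k.** Counted as a failure, the rate is (39 − k)/40. Excluded and replaced by a success, it is (40 − k)/40.

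| k | Counted as failure | Excluded, replaced by a success |
|---|---|---|
| 0 | 39/40 = 97.5%, pass | 40/40 = 100%, pass |
| 1 | 38/40 = 95.0%, pass | 39/40 = 97.5%, pass |
| 2 | 37/40 = 92.5%, **fail** | 38/40 = 95.0%, **pass** |
| 3 | 36/40 = 90.0%, fail | 37/40 = 92.5%, fail |

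The decision changes only at k = 2. The Clopper-Pearson 95% intervals there are:

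- plan's result, 38/40: 83.1 to 99.4%, pass
- counted, no replacement, 37/40: 79.6 to 98.4%, fail
- counted, with a replacement already operated on, 38/41 = 92.7%: 80.1 to 98.5%, fail
- excluded, not replaced, 37/39 = 94.87%: 82.7 to 99.4%, fail

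So with one such subject the change needs a successful replacement. If the replacement fails, the result is 37/40, a fail either way.

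**Several such subjects, with replacements kept.** With one other failure, two are needed: counting one gives 39/41 = 95.1%, pass, and counting two gives 39/42 = 92.9%, fail. With no other failure, three are needed: 40/42 = 95.2% passes and 40/43 = 93.0% fails. In these two cases the plan passes even without replacement (37/38 = 97.4% and 37/37 = 100%).

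**Direction.** An excluded failure is at worst replaced by another failure, so the exclusion cannot turn a pass into a fail.

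**Illustration of size.** Suppose one such subject occurs and is replaced, and let q be the failure rate in everyone else. The chance that the decision changes is P(exactly 2 failures in 39) × P(replacement succeeds) = C(39,2) q² (1 − q)³⁷ × (1 − q), with C(39,2) = 741.

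| q | Basis | Chance |
|---|---|---|
| 0.9% | average failure-related conversion rate in protocol 6.5 (leaves out major complications) | 0.043 |
| 2.7% | top of that range | 0.191 |
| 5% | where the chance is highest | 0.264 |
| 10% | bound implied by the expected completion rate of over 90% in protocol 6.5 | 0.135 |

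These chances are conditional on such a subject occurring.

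**The case against.** **Evaluability comes first.** The objective is that the system performs as intended. After a non-Hugo conversion the operation was finished another way, so the endpoint might be meant to apply only to subjects whose robotic surgery can be assessed. The rule is pre-specified, is repeated consistently in both documents, and was refined in versions 4.0 and 5.0 following regulator feedback. This does not rescue it. The definition joins two conditions, and one breach settles it. Protocol 6.5 itself says, directly after the exclusion, that a complication within 24 hours is no failure unless it is major. Neither document says that a major complication stops counting after a conversion.

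**The case stays visible.** True: such a subject appears in the 30-day major complication rate, the conversion summary and the disposition table. None of these enters the success decision.

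**The event is remote.** This stands in part. A change of decision through a single subject needs a non-Hugo conversion, a major complication within 24 hours in the same patient, exactly two other failures, and a successful replacement. Assuming, purely for illustration, 0.1 to 0.5% such patients, the chance of at least one in 40 is 1 − 0.999⁴⁰ ≈ 4% to 1 − 0.995⁴⁰ ≈ 18%. Multiplied by the conditional 4 to 26%, that is roughly 0.2 to 5% overall. The documents support no particular rate.

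**The correction is one-sided too.** Non-Hugo conversions would enter the primary denominator only when they fail. This also stands and should be disclosed. But applying the definition literally to all FAS subjects, the more coherent alternative, counts this subject as a failure as well.

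**Conclusion.** The concern holds, and the rule should be fixed. It gives a wrong result for a narrow but defined group: subjects converted for non-Hugo reasons who have a Clavien-Dindo grade 3 or higher complication within 24 hours. Their outcome under the plan's own definition is failure, not unknown.

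One such subject turns a fail (37/40 = 92.5%, or 38/41 = 92.7%) into a pass (38/40 = 95.0%) when there are exactly two other failures and the replacement succeeds. These counts need no assumed rates. The conditional chances of 4 to 26% depend on the assumed failure rate in other subjects, and the unconditional chance cannot be derived from the documents. Excluding non-Hugo conversions without such a complication does not inflate the rate under the plan's definition and is not criticised here.

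**What to change.** 1. In protocol 6.5 and 9.1 and SAP 6 and 7.1.3, state that a subject converted for a reason not due to the Hugo system who has a Clavien-Dindo grade 3 or higher complication within 24 hours of surgery counts as not completed in the primary analysis and is not replaced. Limit exclusion and replacement to such conversions without that complication. Apply the same limit to the first PPS exclusion in protocol 9.1 and SAP 7.1.3. Keep the exception for unavoidable adverse events in protocol 8.10.

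2. State in the SAP that inclusion then depends on outcome: a non-Hugo conversion can lower the primary rate but never raise it. Pre-specify a supportive completion rate with a Clopper-Pearson 95% interval in all FAS subjects, in which a non-Hugo conversion is a failure only if it is followed by a major complication within 24 hours. Report it beside the primary result, outside the success decision. With two other failures, one complicated non-Hugo conversion and u uncomplicated ones, the primary rate is 37/40 = 92.50% and the supportive rate is (37 + u)/(40 + u): 92.68% at u = 1 and 93.18% at u = 4. In this example the one-sidedness costs under one percentage point for u up to 4, and the supportive rate reaches 95% only at u = 20 (57/60).

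**Cost.** One rule in four sections and one table row. No new data are needed, since the reason for conversion (protocol 8.5) and the Clavien-Dindo grade (8.5 and 8.6) are already collected. The reported rate may be slightly lower. The protocol change needs MFDS and/or IRB approval with enrolment stopped meanwhile (protocol 12.2), within a three-month window for enrolment and follow-up (protocol 7.1). The supportive row alone could be added by SAP amendment, but it would not correct the success decision.
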